## **INNOVATION**

- This study will novelly assess the effects of the SREC (and potentially other newly available product) aerosols directly in human lungs of smokers who completely substitute the SREC for smoking, and compare this to quitting with NRT.
- The extended use over 10 weeks (8 week intervention) on product that will allow for the subject to learn how to use the product and adjust to adverse effects for two weeks (if any) that are generally short-lived, and allow the lungs to respond over 8 weeks.
- Conducting a trial with serial bronchoscopies before and after the use of the SREC device allows for within-subject comparisons as well as including comparisons to a randomly assigned group.

- The use of multiple endpoints for gene expression (mRNA and miRNA), metabolomics, cell and cytokine changes are comprehensive and complementary. This allows for an integrated assessment for multiple ways that inflammation can happen to distinguish treatment effects.
- This study uses 'omics to assess inflammation, which also provides data for other disease pathways.
- This study will provide new data for the effects of nicotine on pulmonary inflammation using a device demonstrated to deliver nicotine at levels similar to cigarettes.

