**E-liquid Characteristics:**

Nicotine-containing and placebo versions are “tobacco” flavored

Shelf-life at 25C - > 1 year (unopened)

Nicotine concentration - 5% w/w (corresponds to 58 mg / mL)

Propylene Glycol % - ~ 38.75% (wt / wt)

Glycerin % - ~ 50% (wt / wt)

**Product use:** At the first bronchoscopy visit, SREC users will be trained to use the product and given instructions on how to use the device. They will not be requested to use the device at the visit, but to use it at home representing the way real world e-cig users learn to use the product (product use will be observed one week later). An instructional video showing how to use the device may be provided at first bronchoscopy visit, and other visits as needed ([https://www.youtube.com/watch?v=lKcblA\\_AbTg](https://www.youtube.com/watch?v=lKcblA_AbTg)). Similar videos will be created for the other products as needed. Subjects in the SREC arms will be instructed that after two weeks of use, as they

learn to use the product and work towards complete substitution, they will begin their assignment effective on day 15.

E-cig users will be encouraged to use the product every 1-2 hours, and as needed to address cravings. Subjects will be allowed to smoke their usual brand of cigarettes *ad libitum* for the first 2 weeks and encouraged to reduce their cigarettes per day to 5 or less, followed by quitting cigarette smoking and avoiding cannabis use. Subjects will be contacted by phone or email after 72 hours of study product use, and there will be contact with the subject on a weekly basis (phone or visit). This two-week run-in period allows the subject to become accustomed to the product and have a specific quit date.

Subjects randomized to the placebo SREC will be offered varenicline, an FDA-approved smoking cessation medication, at no cost to limit withdrawal symptoms and increase study retention. Those participants will be given the medication at the day 8 visit, one week before the day 15 quit date.

Subjects randomized to NRT complete substitution will be instructed how to use the assigned product(s). Subjects will be asked to use patches (21mg) in combination with gum (4 mg) and/or lozenge (4 mg) . If appropriate, subjects may use a single product after discussion with study staff and/or the study PI. If subjects experience side effects, dosages can be reduced and/or products changed. The NRT group will begin to use the NRT at the day 8 visit, one week before the day 15 quit date.

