## iii. Laboratory Procedures

The following are planned procedures:

- Blood pressure, heart rate and oxygen level
- Physical examination
- Height and weight
- FeNO measurement
- CO measurement
- Pulmonary function tests
- Inhalation assessment
  
- Blood:
  - (1) Glycerol and propylene glycol-- mass spectrometry methods. The assays will be developed and performed in the Nutrient Phytochemical Shared Resource of the OSUCCC, as previously described [182, 183, 290]. Cannabinoids will be measured by mass spectrometry methods [291]. Tetrahydrocannabinol (THC) is a well-established metabolite to confirm abstinence of the consumption of marijuana use.
  - (2) Nicotine boost levels will also be obtained. Subjects will be instructed to use the device immediately prior to the visit. Time of last use will be recorded. Blood will be collected immediately prior to the use of the device. The subject will puff the e-cig using at least three puffs over 10 minutes, and a second blood draw will be done immediately after last puff.
  
- Urine:
  - (1) Pregnancy test for women of childbearing potential (i.e., premenopausal and not surgically sterile).
  - (2) Glycerol and propylene glycol-- mass spectrometry methods. The assays will be developed and performed in the Nutrient Phytochemical Shared Resource of the OSUCCC, as previously described [182, 183, 290].
  - (3) Cannabinoids will be measured by mass spectrometry methods [291]. Tetrahydrocannabinol (THC) is a well-established metabolite to confirm abstinence of the consumption of marijuana use.
  - (4) Tobacco use biomarkers: urine will be analyzed for validation of smoking cessation, the measurement of extent of tobacco use, and assessing exposure. This will include but not limited to: Creatinine; cotinine (metabolite of nicotine), nicotelline, 3-hydroxycotinine, total nicotine equivalents (TNE), polycyclic aromatic hydrocarbons (PAHs, Phe T), total NNAL (metabolite of tobacco-specific nitrosamines), anatabine and anasabine (tobacco alkaloids), mercapturic acids (metabolites of volatile organic compounds) including: 2-HPMA, 3-HPMA, HMPMA, AAMA, CNEMA, HEMA, MHBMA-1+2, MHBMA3, MMA, and S-PMA, 8-iso-PGF2 $\alpha$  (8-isoprostane), 11-dehydrothromboxane B2 (11-dTXB2), PGE-M, Catecholamines, and untargeted metabolomics.
  - (5) Osmolality.
  
- Bronchoalveolar lavage:

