**The Effects of a Standardized Research E-Cigarette on the Human Lung:
A Clinical Trial with Bronchoscopic Biomarkers**

NCT03691350

Statistical Analysis Plan, 09/19/22

SREC SAP

The Specific Aim for this two year project is:

To assess inflammatory changes over 10 weeks (8 weeks experimental condition) for lung and urine biomarkers in smokers in a clinical trial where smokers are randomized to: continued use (n=32), complete switching to the nicotine standardized research electronic cigarette (SREC) (n=32), complete switching to the placebo SREC (n=32), or complete switching to nicotine replacement therapy (NRT) (n=32).

- 1) We will enroll 128 subjects (32 per group). For power calculations, we will use a conservatively planned 66% retention rate at 5 weeks, knowing that we have a 100% retention for never smokers receiving serial bronchoscopies. Thus, the final sample size will be 21 subjects per group (n=84). Although we expect a higher retention rate, we assume 66% to ensure that we have the minimal numbers required to reach meaningful conclusions. Since follow-up samples would not be obtained from subjects that do not finish the treatment protocol, and these samples (inflammation/omics) are our primary outcomes, we cannot use an 'intent to treat' strategy since dropouts will have missing outcome data for any analyses including follow-up measurements (the primary Aim). In light of this, we will compare dropout rates between arms and with demographic/clinical to ensure that the analyses results are not biased by unbalanced dropouts. We will also test for differences in baseline molecular measurements between subjects that dropout after baseline samples are taken vs. subjects that complete the protocol. While we will make every effort to minimize the missing data for this study, missing data can arise due to various reasons. Violation of missing completely at random (MCAR) will be checked by evaluating whether any covariates are associated with missing data. If so, these covariates will be subsequently included and controlled for in the GL(M)M models. In addition, sensitivity analyses will also be conducted using results from multiple imputation.

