- 2) Descriptive statistics and clustering (e.g., principal components analysis [PCA]), will be performed for all biomarker data measured at the different visits. Baseline data (1st bronchoscopy) will then be compared between the four groups (3 conditions and control) using a one-way analysis of variance (ANOVA). The non-parametric Kruskal-Wallis test (continuous or ordinal variables) or the chi-square test (categorical variables) will be applied when the normality assumption of the data is not met. We will compare controls to complete substitution with the SREC (with and without nicotine) or NRT. Generalized linear models (GLM) will be employed with measurement (cell count, gene expression, etc.) as the dependent variable, a covariable for baseline measure, and a main effect of arm. Other relevant variables that are associated with the biomarker results, e.g., baseline smoking, Fagerstrom Test for Nicotine Dependence (FTND), or gender will also be included in our models as they are potential confounders. We also will assess batch effects and include batch as a co-variable in the model (all samples will be analyzed at the same time, except for cell counts). We plan to use baseline molecular measurement as a covariable rather than

modeling the change between baseline and follow-up because the former is more powerful [1]. Given the large dynamic range of the cell count and the 'omics data, we will initially consider a normal distribution. If the data are determined to deviate from normality, we will log-transform the data or assume a non-normal distribution of residuals (such as Poisson) for the GLM. Urine propylene glycol (PG) will be measured at the 2nd bronchoscopy visit and compared to baseline to verify e-cig use. As an exploratory analysis, urinary PG will be used as the exposure predictor variable assessing the biomarker results as dependent variables. Urine anatabine, urine anabasine and nicotelline will be used to confirm complete substitution or a predictor variable for smoking reduction. The cotinine level will be used as a surrogate for smoking reduction.

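### Follow-up cotinine cannot stand in for smoking reduction in the two arms supplied with nicotine (nicotine SREC and NRT)

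*SAP*

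**What the plan says.** SAP item 2 states "The cotinine level will be used as a surrogate for smoking reduction", and protocol section 4.g.i carries the same sentence. Neither names the arms to which it applies or sets a cut-off. In both documents the sentence just before it reads "Urine anatabine, urine anabasine and nicotelline will be used to confirm complete substitution or a predictor variable for smoking reduction".

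The protocol's Laboratory Procedures (section 4.d.iii) describe the analyte as "cotinine (metabolite of nicotine". The SAP's specific aim lists, among the four arms, "complete switching to the nicotine standardized research electronic cigarette (SREC) (n=32" and "or complete switching to nicotine replacement therapy (NRT) (n=32". For the SREC liquid, protocol section 4.c.i gives "Nicotine concentration - 5% w/w (corresponds to 58 mg / mL". For the NRT arm it says "Subjects will be asked to use patches (21mg) in combination with gum (4 mg) and/or lozenge (4 mg". The Innovation part of the protocol's background describes the work as "using a device demonstrated to deliver nicotine at levels similar to cigarettes". The Potential Risks section (4.f.i) says that NRT, alone or combined, usually supplies less nicotine than smoking does.

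The arm comparison in SAP items 2 and 3 models the follow-up measure on its baseline value and arm, with possible further covariates. Follow-up cotinine is not named as a term.

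**The concern.** A marker of smoking reduction should fall when cigarettes fall, and by the same amount whichever arm the participant is in. Cotinine does this only where cigarettes are the main source of nicotine. Two of the four arms replace cigarette nicotine with product nicotine, so the same change in smoking gives a different change in cotinine depending on assignment. The error is systematic by arm and would not average out as noise.

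The comparison most exposed is nicotine SREC against placebo SREC, which addresses the protocol's hypothesis that nicotine dampens the inflammatory effect of the aerosol. If both arms stopped smoking equally well, cotinine would still suggest much more residual smoking in the nicotine arm. An analyst using it to explain or qualify a biomarker difference between these arms would be mistaking the assigned exposure for continued smoking.

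**Working it through.** The plan attaches no figure to this sentence, so there is nothing to reproduce. The check is a comparison of the passages and simple arithmetic.

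**Share of the trial affected.** The SAP plans 32 per arm randomised and 21 per arm completing. Two arms are supplied with nicotine: 32 + 32 = 64 of 128 randomised (50%), and 21 + 21 = 42 of 84 completers. This counts people for whom the marker is unsuitable. It is not a count of people who would be misclassified.

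**Direction and size of the error.** Let *s* be the fraction of baseline cigarettes still smoked at follow-up, and *f* the nicotine obtained from the assigned product as a fraction of baseline cigarette nicotine. Assume that cotinine is proportional to total nicotine intake and that there is no other nicotine source. Then:

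- true smoking reduction = 1 − *s*
- apparent reduction by cotinine = 1 − (*s* + *f*)
- understatement = *f*, whatever the value of *s*

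For a complete switcher (*s* = 0, true reduction 100%):

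| Arm | *f* | Basis for *f* | Apparent reduction |
|---|---|---|---|
| Placebo SREC | 0 | no nicotine supplied | 100% |
| Nicotine SREC | about 1 | protocol's Innovation text, taken at face value | about 0% |
| NRT | 0.3 to 0.9 | assumed range; documents say only that delivery is usually below smoking | 70% down to 10% |

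With identical abstinence, the two SREC arms would therefore differ by about 100 percentage points in apparent smoking reduction (100% − 0%).

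**Ordering of participants.** Take someone who uses no product and halves their smoking: *s* = 0.5, *f* = 0, apparent reduction 50%. A complete nicotine-SREC switcher at *f* of about 1 reads as about 0%, so the order is reversed. A complete NRT switcher ranks below the 50% participant only if *f* exceeds 0.5. At *f* = 0.3 the reading is 70% and the order is preserved.

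**Where cotinine remains valid.** The control and placebo-SREC arms are supplied with no nicotine product, so *f* = 0 and cotinine can follow smoking. The baseline dose-response analysis in SAP item 8 uses samples taken before any product is used, in people who smoke, with current NRT use excluded and recent e-cigarette use limited by the eligibility criteria. The problem does not arise there.

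**The case against.** The strongest reply is that the plan does not rely on cotinine to decide who switched. The sentence immediately before gives that task to anatabine, anabasine and nicotelline, and also names them as predictors of smoking reduction. Exhaled CO is recorded daily as a further check. A reader might infer from the cotinine sentence that complete switchers would be classed as still smoking. The documents do not support this: no rule in either one classifies, includes or excludes anyone by cotinine.

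A reader might also infer that the primary biomarker contrasts are biased. They are not. The model uses the baseline measure and arm, and all three intervention arms are compared with control without a follow-up cotinine term. The follow-up exposure predictor that the SAP names for its exploratory analysis is urinary propylene glycol.

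Nor should the two nicotine arms be treated alike. The protocol expects NRT to deliver less nicotine than smoking, so a partial apparent reduction is the likely reading there. The protocol's dispensing assumption gives 0.5 pod/day × 1.9 mL × 58 mg/mL = 55.1 mg of nicotine per day in the liquid consumed. That is not absorbed dose and does not measure the bias.

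All of this stands, and it limits the consequence. It does not make the sentence right. The plan is left with two measures of one construct that will disagree systematically in half the trial, and nothing says which prevails.

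**Conclusion.** The sentence is wrong as written, and the matter is of moderate importance. In the nicotine-SREC and NRT arms follow-up cotinine measures total nicotine intake and would understate smoking reduction. For a complete nicotine-SREC switcher it would miss nearly all of the reduction if delivery is similar to cigarettes. On NRT it would miss a smaller part that the documents do not quantify.

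What is affected is the description of exposure and compliance, and any comparison of smoking reduction across arms, above all nicotine against placebo SREC. The primary arm comparison, the verification of switching and the baseline dose-response analysis are not affected.

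The sizes rest on cotinine being proportional to nicotine intake, on the protocol's own statement about SREC delivery, on an assumed range for NRT, and on no nicotine from outside the study. The direction needs only that the supplied products deliver some nicotine.

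**What to change.** Amend the sentence in SAP item 2 and in protocol section 4.g.i so that:

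- follow-up cotinine serves as a smoking-reduction surrogate only in the control and placebo-SREC arms;
- in the nicotine-SREC and NRT arms it is reported as total nicotine exposure;
- smoking reduction in all four arms is based on anatabine, anabasine and nicotelline, supported by the exhaled CO already collected, which currently has no role in the SAP.

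Leave the baseline cotinine analysis in SAP item 8 as it is. While the text is open, it would help to state cut-offs for these markers and what happens when they disagree, since the SAP gives neither.

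The cost is a short text amendment to two documents. No new assay, visit or change in sample size is needed.

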### **iii. Specimen collection timeline**

Specimens will be collected at baseline bronchoscopy (day1) and follow-up bronchoscopy (~day 71).

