## g. Statistical Methods

### i. Data Analysis Plan

The analytical plan does not change due to the increase in intervention period from 4 to 8 weeks.

Descriptive statistics and clustering (e.g., principal components analysis [PCA]), will be performed for all biomarker data measured at the different visits. Baseline data (1st bronchoscopy) will then be compared between the four groups (3 conditions and control) using a one-way analysis of variance (ANOVA). The non-parametric Kruskal-Wallis test (continuous or ordinal variables) or the chi-square test (categorical variables) will be applied when the normality assumption of the data is not met. We will compare controls to complete substitution with the SREC (with and without nicotine) or NRT conditions. Generalized linear models (GLM) will be employed with measurement (cell count, gene expression, etc.) as the dependent variable, a covariable for baseline measure, and a main effect of arm. Other relevant variables that are associated with the biomarker results, e.g., baseline smoking, FTND, or gender will also be included in our models as they are potential confounders. We also will assess batch effects and include batch as a co-variable in the model (all samples will be analyzed at the same time, except for cell counts). We plan to use baseline molecular measurement as a covariable rather than modeling the change between baseline and follow-up because the former is more powerful [300]. Given the large dynamic range of the cell count and the 'omics data, we will initially consider a normal distribution. If the data are determined to deviate from normality, we will log-transform the data or assume a non-normal distribution of residuals (such as Poisson) for the GLM. Urine PG will be measured at the 2nd bronchoscopy visit and compared to baseline to verify e-cig use. As an exploratory analysis, urinary PG will be used as the exposure predictor variable assessing the biomarker results as dependent variables. Urine anatabine, urine anabasine and nicotelline will be used to confirm complete substitution or a predictor variable for smoking reduction. The cotinine level will be used as a surrogate for smoking reduction.

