Understanding the epigenomic/genomic/proteomic/environment context and regulation of metabolic phenotypes will expand our knowledge of the effects of e-cig on lung biology, and could contribute to finding successful interventions, including accurate predictions of e-cig related adverse effects. Typical omics integration methods include logistic regression or correlations among omics measurements (when measured in the same samples), intersection of gene/protein/metabolite lists (when measured in different samples), or further downstream integration by assessing alterations in pathways [309-311]. Because our omics measurements will be made in the same sample, we will be able to directly assess relationships between our molecular data through regression or correlation analyses. Of note, typical regression/correlation approaches are not appropriate for low sample numbers, and they do not readily adjust for differences in sample size between phenotype groups or for potential confounders. Another approach, which we propose here, is to directly test whether associations between miRNA or gene or cytokine and metabolite levels are specific to a group assignment. To test this, we will apply a novel linear model approach recently developed by [name] for these types of analysis:  $m = g + t + g:t$ , where  $m$  are metabolite abundances,  $g$  are miRNA or gene or cytokine levels,  $t$  is treatment group (e.g. SREC vs. continued smoking), and  $g:t$  is the interaction between miRNA or gene or cytokine level and treatment group. A statistically significant  $g:t$  interaction p-value would indicate that gene (or miRNA or cytokine):metabolite relationships are present in one treatment group and not the other. Pathway enrichment analysis of associated miRNA, genes,

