Understanding the epigenomic/genomic/proteomic/environment context and regulation of metabolic phenotypes will expand our knowledge of the effects of e-cig on lung biology, and could contribute to finding successful interventions, including accurate predictions of e-cig related adverse effects. Typical omics integration methods include logistic regression or correlations among omics measurements (when measured in the same samples), intersection of gene/protein/metabolite lists (when measured in different samples), or further downstream integration by assessing alterations in pathways. Because our omics measurements will be made in the same sample, we will be able to directly assess relationships between our molecular data through regression or correlation analyses. Of note, typical regression/correlation approaches are not appropriate for low sample numbers, and they do not readily adjust for differences in sample size between phenotype groups or for potential confounders. Another approach, which we propose here, is to directly test whether associations between miRNA or gene or cytokine and metabolite levels are specific to a group assignment. To test this, we will apply a novel linear model approach recently developed by [name] for these types of analysis: $m = g + t + g:t$, where m are metabolite abundances, g are miRNA or gene or cytokine levels, t is treatment group (e.g., SREC vs. continued smoking), and g:t is the interaction between miRNA or gene or cytokine level and treatment group. A statistically significant g:t interaction p-value would indicate that gene (or miRNA or cytokine):metabolite relationships are present in one treatment group and not the

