
methylation levels and corresponded cytokines. Correlations controlling for possible confounders (e.g., age) will be explored using multiple linear regression models. We will also explore if the correlation between methylation and cytokine levels may be mediated by gene expression of cytokines using interaction analysis.

- 3) To compare treatment groups at follow-up for inflammatory markers and 'omics data, we will use generalized linear models (pairwise) with a covariable for baseline measure to account for baseline differences:

$$\text{Model 1: Followup_Measure} = \text{Baseline_Measure} + \text{arm} + e.$$

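### The omics integration model m = g + t + g:t reads a slope difference as a relationship present in one arm only, and it names no visit and carries no baseline term

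*SAP*

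**What the plan says.** Protocol section 4.g.i proposes to "directly test whether associations between miRNA or gene or cytokine and metabolite levels are specific to a group assignment". SAP item 2 repeats the proposal. Both give the model m = g + t + g:t, "where m are metabolite abundances, g are miRNA or gene or cytokine levels, t is treatment group". Neither says which visit m and g come from, and neither lists a baseline term.

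The SAP's decision rule reads: "A statistically significant g:t interaction p-value would indicate that gene (or miRNA or cytokine):metabolite relationships are present in one treatment group and not the" other. Features in these associations go on to pathway enrichment and to the models that predict treatment group.

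Elsewhere the plan uses the baseline sample. For the arm comparisons the Protocol states: "We plan to use baseline molecular measurement as a covariable rather than modeling the change between baseline and follow-up because the former is more powerful". SAP item 2 says the same. SAP item 3 (Model 1) specifies "generalized linear models (pairwise) with a covariable for baseline measure to account for baseline differences", and item 4 applies Model 1 to mtDNA. Item 5, which also relates one molecular feature to another, carries baseline expression. Item 7, the tissue-by-arm interaction, carries the baseline measure. On timing, the Protocol's specimen timeline reads "Specimens will be collected at baseline bronchoscopy (day1) and follow-up bronchoscopy (~day 71"), and its Table 3 lists the same BAL and brushing assays at both bronchoscopies.

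**The concern.** There are two separate issues.

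**Interpretation.** The g:t coefficient is the difference between two slopes. Rejecting zero for that difference says nothing about whether either slope is zero. A relationship that is strong in one arm and moderate in the other can give a significant g:t, and so can slopes of opposite sign. The plan would report each as present in one arm and absent in the other, and the pathway results would be described on that basis.

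**Specification.** With no visit named, two analysts could fit different models. If m and g are second-bronchoscopy values, stable between-subject differences in metabolite level stay in the error term, although a baseline value is available to remove part of them. The test compares slopes with about 21 subjects per arm, so precision is limited. The SAP gives no reason for treating this model differently from items 3, 4, 5 and 7.

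**Working it through.** **Inputs from the documents.** Analysed sample: "the final sample size will be 21 subjects per group (n=84"), so 42 subjects for a two-arm model. The planning threshold for omics is 0.0001, two-sided (SAP item 3). Item 3 adds that FDR will be used in practice. Neither rule is restated for g:t.

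**Inputs not in the documents.** The visit-to-visit correlation (rho), the slopes, the alpha and the target power for g:t. All are assumptions below.

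**Step 1: nearest stated figure.** The plan gives no power for g:t. For arm comparisons it gives 80% power at 2.1-fold with CV 0.5, 21 per arm and alpha 0.0001. On the log scale SD = sqrt(ln(1 + 0.5²)) = sqrt(0.223) = 0.472. A two-sample noncentral t with 40 df reaches 80% at 2.14-fold, which agrees with 2.1 to the printed decimal. This confirms the planning framework but does not transfer to a slope contrast.

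**Step 2: the interpretation rule.** Let m = b·g + e with unit variances for g and e, b = 0.75 in one arm and 2.5 in the other. Within-arm correlations are b/sqrt(1 + b²): 0.75/sqrt(1.5625) = 0.60 and 2.5/sqrt(7.25) = 0.93. Both arms have the relationship. The OLS test of g:t at alpha 0.0001, 21 per arm, was significant in 79% of simulated trials.

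**Step 3: adding baseline terms.** Follow-up m = b·g + e, with b = 0 in one arm and 1.75 in the other. Both g and e correlate rho across visits. The model as written has 42 - 4 = 38 residual df. With m_baseline and g_baseline it has 36. Results from 20,000 trials per setting, alpha 0.0001:

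| rho | as written | with baseline m and g | change (points) |
|---|---|---|---|
| 0.1 | 79.1% | 75.7% | -3.4 |
| 0.3 | 79.4% | 81.2% | +1.8 |
| 0.5 | 79.1% | 89.3% | +10.2 |
| 0.7 | 79.6% | 98.2% | +18.6 |

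An independent repeat gave 79% and 75%, 80% and 81%, 80% and 90%, 79% and 98%. Null rejection at alpha 0.05 was 4.7% to 5.3%.

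*Analytic check.* If baseline removes a share rho² of the residual variance, power = Φ((z_a + z_0.80)/sqrt(1 - rho²) - z_a). At alpha 0.0001 and rho 0.5 this is Φ((3.891 + 0.842)/0.866 - 3.891) = Φ(1.57) = 94%. The simulated gain is smaller because the formula ignores the small-sample t reference and the degrees of freedom spent.

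**Step 4: sensitivity.** All at alpha 0.0001 and rho 0.5.

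- *Weaker link in one arm, none in the other.* Within-arm correlation 0.5: 1.3% to 1.9%. Correlation 0.6: 3.9% to 6.9%. Correlation 0.7: 12.8% to 20.5%. The Step 3 contrast corresponds to 1.75/sqrt(4.0625) = 0.87 against 0.
- *Link present at baseline in both arms and lost in one.* 80.1% as written, 82.5% with baseline m alone, 90.1% with baseline m and g. Both terms are needed.
- *Baseline terms allowed to differ by arm.* Power falls from 79.4% to 70.6% when the link is new, and from 80.1% to 71.2% when it is lost. The loss is about 9 points (about 8 in a further run, 79% to 71%).

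**The case against.** **The formula may be shorthand.** SAP item 2 says that variables associated with the biomarker results, and batch, will enter the models. It also faults the usual correlation methods for not readily adjusting for confounders. A reader could take the formula as a core to which covariates are added. But the covariate statement is made for the arm-comparison GLM and does not expressly cover g:t. The objection shows that the specification is open, which is a reason to settle it.

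**The visit is unstated, so one cannot say that baseline is ignored.** This stands. A reader might infer that the plan treats the second-bronchoscopy samples as a stand-alone cross-section. The text does not say so. It is only the likeliest reading, because randomization takes place at the first bronchoscopy before the procedure and those samples carry no treatment effect.

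**The power loss is not a property of this plan.** This also stands. It is tempting to say that the test gives up about 10 points of power. The documents give no visit correlation, effect size or alpha for g:t, and the 10 points require rho 0.5 and a within-arm correlation of 0.87 against 0. For weaker links the test is badly underpowered with or without baseline.

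**Adjustment changes the question.** The plan asks about associations between levels, whereas the adjusted slope is conditional on prior levels. The power argument in item 2 concerns the arm effect and does not carry over automatically. Both points are fair and belong in the SAP.

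**This is exploratory screening with no power claim, and type I error is unaffected.** True, and it limits the weight of the baseline point. It does not excuse the interpretation rule, which is wrong whatever the power.

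**Conclusion.** The interpretation sentence is an error and needs no assumption to establish. A significant g:t means different slopes. The 79% in Step 2 illustrates how readily the false label can arise and is not an estimate for this trial.

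The missing visit and baseline term are a gap in specification and an unexplained departure from the SAP's other treatment models. Adding common baseline m and g is a cheap improvement whose benefit depends on quantities that the documents do not give. With 21 per arm, alpha 0.0001 and slopes of 0 and 1.75, the change runs from about -3 points at rho 0.1 to +19 at rho 0.7. At rho 0.5 it is 0.6 to 7.7 points for within-arm correlations of 0.5 to 0.7. It becomes a loss of about 8 to 9 points if the baseline terms vary by arm. No stated power figure in the plan is shown to be wrong by this point.

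**What to change.** In SAP item 2 and Protocol section 4.g.i:

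1. Replace the interpretation sentence with one saying that a significant g:t means that the slope of m on g differs between the arms compared. Report each arm's slope with its confidence interval before calling a relationship present or absent, or a feature treatment-specific. An interval that includes zero does not by itself show absence, least of all with 21 per arm.
2. Name the visit and write the model as m_followup = g_followup + t + g_followup:t + m_baseline + g_baseline, fitted to second-bronchoscopy values. Keep the two baseline terms common to the arms and test g_followup:t. If the sponsor prefers to omit them, say why.
3. State that the tested slope is conditional on baseline levels, and give the multiplicity rule for the g:t tests.

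The cost is wording, two covariates and two degrees of freedom per model. No new samples or assays are needed. The risk is a small loss of power for features with low visit-to-visit correlation, about 3 points at rho 0.1. The choice should be fixed before follow-up data are examined, so that it is not made feature by feature.
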